- Once the music play duration has lapsed, the study subject will be asked to then reassess their anxiety level on the same 1-10 scale as pre-music intervention. This reassessment will be performed at three event points: directly following completion of music duration, just prior to transport to the OR, and directly upon arrival in the OR. STAI questionnaire completion will be assessed only directly following completion of the intervention, not before transport to the OR or upon arrival in the OR. Heart rate and blood pressure measurements will be recorded at all three post-intervention assessments. After completion of the final post-music assessment, this will conclude the study subject’s participation.
- Pre- and post-music anxiety scores will be recorded and correlated to the study subjects’ assigned 3-digit codes.
- Once all 30 (or 33 maximum) subjects in each intervention group have undergone the study protocol, their pre- and post-anxiety data will be analyzed.

Please also describe the following concerning procedures:

- a. *How individuals will be screened for eligibility. Specify screening that will take place prior to informed consent and screening that will take place after informed consent:*
Patients will be screened for eligibility by the PI or Co-I and will be required to meet all inclusion criteria and none of the exclusion criteria. To do this, a brief chart review will be performed to assess age and ASA clinical status, and to ensure that daily anxiolytic medications are not taken at baseline. After informed consent, the first 0-10 anxiety rating and STAI questionnaire will be completed by the participant. If their anxiety score is rated as 0, then at that time they will be excluded from participating in the study.
- b. *Procedures being performed to monitor subjects for safety or to minimize risks:*
As stated above, the PI or Co-I will remain nearby to continually assess volume status of the music to prevent potential tympanic membrane injury.
- c. *The source records that will be used to collect data about subjects. (Submit all surveys, scripts, and data collection forms.):*
See attached data collection and anxiety-screening forms

2. *Is there a placebo control arm?*
 Yes No
3. *Describe the following concerning pregnancy testing and birth control:*
 - a. *What type of pregnancy testing and how frequently will be conducted on women of reproductive potential. If testing will not be conducted provide the reason:*

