Pregnancy testing will not be conducted, as it would be redundant since only patients already admitted to the Tufts Medical Center Labor and Delivery Unit who are scheduled for cesarean section will be approached and recruited for this study.
 - b. *What birth control methods women of reproductive potential will be instructed to use. If women will not be instructed about acceptable methods of birth control, clarify why:*
Birth control methods will not be discussed as part of this study. These discussions will be left to be had between the patients and their OB/Gyn or primary care providers.
 - c. *What birth control methods men of reproductive potential will be instructed to use. If men will not be instructed about acceptable methods of birth control, clarify why:*
This study will only enroll participants of female sex. If female-sex-assigned-at-birth subjects identify their gender as male, their discussions surrounding birth control will be left to be had between them and their OB/Gyn or primary care providers.
4. *Describe the data that will be collected during the study and how the data will be obtained:*
The data collected during this study will include patient age, race, ethnicity, height, weight, gestational age, gestational history, ASA status, blood pressure and heart rate measurements, and cesarean delivery type (scheduled vs. unscheduled). This data will be obtained through a combination of chart review, oral history taking from the participant, and physical measurement (for blood pressure and heart rate) by the investigator. Anxiety ratings on a 0-10 scale and an STAI scale will also be collected by the investigator.
 - a. *If there are plans for long-term follow-up (once all research related procedures are complete), describe the data will be collected during this period:* N/A
5. *Specify which procedures, tests, visits, etc. described above are:*
 - a. *Part of usual standard of care at Tufts:*
Acquisition of heart rate and blood pressure measurements are part of the standard of care at Tufts Medical Center, as are the determinations of age, race, height, weight, ethnicity, gestational age, gestational history, and ASA status.
 - b. *Performed solely for research purposes:*
Anxiety ratings on the 0-10 scale and STAI scale will be performed solely for research purposes.

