6. *For Humanitarian Use Device (HUD) uses provide a description of the device, a summary of how you propose to use the device, including a description of any screening procedures, the HUD procedure, and any patient follow-up visits, tests or procedures* N/A

F.3 Evaluations

Will you perform any laboratory tests for this study?

Yes No

F.4 Collection, Storage, and Use of Human Biospecimens for Unspecified Future Research (formerly referred to as “Tissue Banking”)

Will biospecimens be collected and stored for unspecified future research?

Yes No

G. Ethics and Protection of Human Subjects

G.1 Informed Consent Process

Will subjects be required to provide informed consent?

Yes No

If Yes, respond to all of the following:

1. *Where the consent process will take place (e.g. a private clinic room):*
The informed consent will be taken in-person in the pre-op area in a private room.
2. *Anticipated amount of time a potential subject will have to make a decision about participation in the study:*
The patient is anticipated to decide within roughly 15 minutes. However, this is not a cutoff and it will be ensured that patients will not be coerced and will be given ample time to think about enrollment.
3. *Processes to ensure ongoing consent throughout the study:*
The researcher will be present for the entirety of the study intervention and will be able to stop the intervention at any point if the patient wishes to discontinue their involvement. Patients will also be informed that they are able to withdraw from the study at any time.
4. *Role of each research team member involved in the informed consent process (Please note, in general, for studies designated by the IRB as greater than minimal risk, a physician PI or Co-I must perform the informed consent process with subjects. A study coordinator/clinical research associate may not consent subjects. A study coordinator/clinical research associate may assist with this process; however, the PI or Co-I should be present to discuss the study with the subject and answer questions, and the PI or Co-I should sign the ICF documenting that s/he has performed the informed consent process with the subject and the subject understands the study.):*
Either the PI or Co-I will perform the consent process.
5. *Check to confirm you will follow “[SOP: Informed Consent Process for Research \(HRP-090\)](#)”.*

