prevented via software functions in the original generation of three-digit numbers. No part of the patient's information or MRN will be used to generate the randomly generated number. Once this unique, randomly generated 3-digit number has been assigned, all coded information will utilize this unique identification number. The 3-digit number will replace the patient's MRN on coded data. The only place where the patient's MRN and their unique 3-digit identification number will coexist is on the physical key that will be kept in the PI's locked office as detailed in section G.3.1. Coded data will be stored with a Tufts CTSI REDCap account. Records will be stored for 7 years after the study is closed with the IRB, per IRB policy. The key will be immediately destroyed once the required number of participants have been recruited and the data compiled.

3. *Describe any procedures that will be used for quality control of collected data:* continual collaboration between PI and Co-I on data collection and handling.

I.5 Randomization

Will subjects be randomized?

Yes No

If Yes respond to all of the following:

1. *Describe the randomization procedures, including the ratio of subjects randomized to each study arm:*
Randomization will be performed to assign study subjects to one of the two intervention groups using “randomizer.org” or a similar online program. This will also assign subjects to a random number to help blind later analysis. Ratio of subjects should be 50/50 in each study arm. Determination of music dosage (the duration of music played for participant listening) will be done using the biased coin up-down sequential allocation algorithm, which is not random.
2. *Describe the blinding procedures:* The PI or Co-I administering the study intervention will be unable to remain blind to the study intervention given the inherent nature of the protocol. This will also be true of the participants, as the intervention treatment arms will likely be easily distinguishable. However, the participants will remain blind to their randomized intervention group until the intervention begins. Given the nature of clinical workflow surrounding cesarean sections, blinding of anxiety level assessment will also not be feasible.

J. Drugs or Devices

1. Will the research involve drugs?

Yes No

2. Will the research involve devices?

Yes No

K. Study Administration

K.1 Setting

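### An unblinded investigator, whose next allocation depends on the response, collects the post-music anxiety rating, and the plan has no step to limit interviewer influence, although concealed self-entry by the participant would be cheap.

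*Combined protocol and SAP*

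**What the plan says.** - **Who collects the rating.** Section F.2, item 4 (data collected): "Anxiety ratings on a 0-10 scale and an STAI scale will also be collected by the investigator". This covers all ratings, baseline included.
- **Who is blind.** Section I.5, item 2: "The PI or Co-I administering the study intervention will be unable to remain blind to the study intervention". On participants it adds: "This will also be true of the participants, as the intervention treatment arms will likely be easily distinguishable". On the rating itself, citing clinical workflow, it says that "blinding of anxiety level assessment will also not be feasible".
- **What blinding is planned.** Section I.5, item 1, on the random number given to each subject: "This will also assign subjects to a random number to help blind later analysis". Section I.5 also keeps participants unaware of their arm until the music begins.
- **How duration is set.** Section I.5, item 1: it "will be done using the biased coin up-down sequential allocation algorithm, which is not random".
- **Baseline rating.** Section F.2, item 1(a): "the first 0-10 anxiety rating and STAI questionnaire will be completed by the participant".
- **Post-music rating.** Section F.2, item 1 says only that the subject is asked to reassess. It does not say whether the answer is spoken or written.
- **Staffing.** Section K.3 gives a team of two. Under K.2 the Co-I handles eligibility, consent and the study procedures. Section G.1, on ongoing consent, adds: "The researcher will be present for the entirety of the study intervention".

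**The concern.** The primary endpoint (section I.1) is an ED95 built from a subjective score given just after the music, in the presence of the person who supplied it. That person knows the arm and the duration and, under an up-down design, what a response or non-response means for the next participant. In such a setting, tone, prompting or the participant's wish to please can move a rating slightly, and a slight move may be enough to reclassify a result: the preliminary signal in section B.1 is a fall of only 1 point.

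The random number helps blind the later analysis. It cannot protect a rating at the moment it is given. Because the investigator also knows the arm, any shading could differ between Mozart and preferred music and so affect the secondary comparison of the two ED95s.

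**Working it through.** **1. Size of an arm.** Section I.2 enrols 33 per group and expects about 10% attrition: 33 × 0.9 = 29.7, about 30. The plan's figure reproduces, so n = 30 is used below.

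**2. How many non-responses carry the estimate.** Suppose all 30 were treated exactly at the true ED95. This is a simplification, since a sequential design spreads participants over several durations.
- Expected non-responses: 30 × 0.05 = 1.5.
- P(none) = 0.95^30 = 0.215.
- P(exactly one) = 30 × 0.05 × 0.95^29 = 0.339.
- P(one or none) = 0.215 + 0.339 = 0.554, about 55%.

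One non-response recorded as a response can thus remove much of the information at that duration.

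**3. Direction.** The protocol names the biased-coin design but does not write out its rule. Assume the usual form for an ED95: a non-response moves the duration up, and a response moves it down with probability 0.05/0.95 = 0.053 and otherwise leaves it. A false response then mainly prevents an upward step, so the estimate is pulled down.

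**4. What a recorded ED95 would mean.** Let a share f of true non-responses be recorded as responses. The documents give no f. With true response probability p, the recorded probability is p + f(1 − p). Setting this to 0.95 gives p = 1 − 0.05/(1 − f).

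| f (assumed) | True response at the recorded ED95 |
|---|---|
| 0.10 | 94.4% |
| 0.20 | 93.8% |
| 0.30 | 92.9% |
| 0.50 | 90.0% |

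Errors the other way overstate the ED95. If a share g of true responses is recorded as non-responses, the true response needed for a recorded 95% is 0.95/(1 − g): 96.0% at g = 0.01 and 100% at g = 0.05.

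**5. Illustration in minutes.** A simulation used an assumed logistic curve (ED50 6 min, ED95 15 min), a start at 4 min, 2-min steps, the rule in step 3, n = 30 and an isotonic estimate, with 4,000 runs per setting. Only the 4-min start has a basis in the documents (section B.1).

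| f (assumed) | Median ED95 estimate (min) | Change from f = 0 (min) |
|---|---|---|
| 0 | 13.4 | – |
| 0.20 | 13.0 | −0.4 |
| 0.30 | 12.0 | −1.4 |
| 0.50 | 11.1 | −2.3 |

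The estimate at f = 0 is already below the assumed 15 min, so only the changes are informative. They confirm the direction; they do not measure the bias in this trial.

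**6. Is a remedy feasible?** Section F.2 already has the participant complete the same scale and the STAI at baseline and refers to written forms. Clinical workflow may rule out a separate assessor. It does not explain why she could not mark her own form in the pre-operative area directly after the music.

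**The case against.** The strongest reply is that the protocol is right and open about it. The 0-10 score is a self-report, and the participant hears her music and experiences its duration, so no mode of entry blinds the rating. That stands. A reader might infer that the blinding statement is wrong and should go; the documents do not support this, because it is a true disclosure. What is missing is mitigation alongside it.

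Second, a reader might infer from section F.2 that the mode changes, with self-completion at baseline and an interview afterwards. This is not established. The same section also has subjects asked for their rating at baseline, and the sentence on collection by the investigator covers every time point. It may only mean collecting a form that the participant filled in. The forms are referred to as attachments and are not part of the text, so the post-music mode is simply not stated.

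Third, the up-down rule and the threshold for a response are not written out. The dependence of the next duration on the rating follows from the named design, not from a stated rule.

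Fourth, the workflow argument has force for the ratings just before transport and on arrival in the OR. It has little force for the rating directly after the music.

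Finally, the statement in G.1 about the researcher's presence concerns ongoing consent. It shows presence during the music, not how the rating is taken.

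**Conclusion.** The point holds as a cheap improvement, not as a flaw that invalidates the design. An unblinded investigator with an active part in the sequence collects the response on which the primary endpoint depends, and the protocol body gives no self-entry, concealment or script for the post-music rating. With about 1.5 non-responses expected among 30 at the true ED95, the estimate is sensitive to individual ratings.

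The conclusion that the ED95 would be understated rests on two assumptions: that participants shade towards improvement, and that the usual biased-coin rule applies. The size cannot be derived from the documents. A reader might be tempted to take the 4 minutes per 1-point fall in section B.1 as a slope, so that a 0.25-0.5 point shift becomes 1-2 min. The documents do not support that: they report a single preliminary result, give no source for such a shift, and leave the dose-duration relationship as an exploratory objective (section C).

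**What to change.** Keep the statement in I.5 that blinding is not feasible, and add a short procedure to F.2 and I.5:

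- Directly after the music, the participant records the 0-10 rating and the STAI herself on the paper form, or in REDCap if a device is available. Her baseline score is out of view, and the investigator does not see the new score until she has finished.
- The baseline rating is taken in the same way.
- The investigator uses a fixed, neutral script that does not suggest a fall is expected.
- Self-entry is used before transport and on OR arrival only where workflow allows, and the mode used is recorded.
- Remaining expectation bias is stated as a limitation.

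A fixed form would also settle the scale, which F.2 gives as 0-10 before the music and 1-10 after it.

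The cost is a short script and a few seconds per rating, with no extra staff. A tablet is not mentioned in the documents and is not needed. If the attached forms already provide for concealed self-entry, one sentence saying so covers the mode; the script and the limitation would still need to be added.

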1. *Describe the criteria that define who will be excluded in the study as a numbered list:*
 1. Patient refusal.
 2. Impaired hearing.
 3. Patient is taking at least one anxiolytic medication daily at baseline.
 4. No anxiety (a score of 0, on a scale of 0-10 of pre-music exposure anxiety) after consent is given.
 5. ASA physical status rating of IV or higher. (Incapacitating disease that is a constant threat to life; a moribund patient who is not expected to live 24 hours with or without surgery)
 6. Severe medical condition(s) of the fetus or other pregnancy complications (ex: congenital heart defects, physical malformations, pre-term delivery, etc.)
2. *Describe in detail how the eligibility criteria will be assessed and satisfied (e.g., medical record review, physical examination):*
A brief medical record review, discussion with the patient, and pre-music anxiety assessment (after consent is given) will be performed.
3. *State who will determine eligibility. Note that those who are designated to determine eligibility must have appropriate training, expertise, and oversight, for example a physician PI or Co-I on a biomedical study:*
Either the PI or Co-investigator will determine final eligibility.
4. *Can study subjects participate in another research study while participating in this research study:*
 Yes No

D.3 Withdrawal of Subjects

1. *Describe anticipated circumstances under which subjects will be withdrawn from the research without their consent:*
Participants who score a 0 on their pre-music anxiety assessment will be withdrawn from the study.
2. *Describe procedures that will be followed when subjects withdraw voluntarily or are withdrawn from the research, including the possibility of partial withdrawal from study intervention with continued data collection:*
Participants who are withdrawn from the study will be provided the standard of care at Tufts Medical Center. All collected data and identifying information will be promptly destroyed.
3. *Describe any necessary safety precautions to be applied to subjects who withdraw or are withdrawn (tapering drug doses, evaluative x-ray, etc.):*
 N/A

D.4 Recruitment and Retention

D.4.1 Local Recruitment Methods

Describe the following attributes of the recruitment plan for the local Tufts site:

1. *When, where, and how potential subjects will be recruited:*
 - a. *Source of subjects (for example, patient population, local community, etc.):*

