- Once consent is given, the study subjects will be asked to assess their anxiety level on a scale of 0-10, 0 being no anxiety at all. Additionally, they will be asked to complete 6 STAI questionnaire prompts to further assess their anxiety levels. If the score is 0, they will automatically be removed from the study (as per the exclusion criteria). If the score is greater than 0, a baseline heart rate and blood pressure will be recorded, and the participant will proceed to the study intervention.
- All study participants will be also initially asked to choose four songs of personal preference that they would enjoy listening to. These song choices will be written down on their pre-intervention screening questionnaire and later used if their pre-determined music selection falls into the “personal preference” study arm.
- If there are multiple support people present in the room, the participant will be asked to identify a maximum of one person to stay in the room for the study intervention.
- The study intervention includes listening to pre-selected music, randomized to selections either from Conrad, et al. or from their own preference list, for a pre-determined duration ranging from 1-30 minutes. This intervention is being performed exclusively for research purposes and is not part of the standard of care. The study subjects will listen to this music played from a speaker connected to an audio device, both supplied by the research team. The investigator and patient will collaborate on patient positioning (supine, semi-recumbent, seated upright, etc.) to optimize patient comfort during the study intervention. Active participation on the study subjects’ part will be required to continually assess the volume of the music being played to avoid potential tympanic-membrane injury.

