4. *In this study, will you be entering research data using a computer software application (on a computer or any other electronic device)?*

Yes No

If Yes, respond to the following:

- a. For **Tufts Medical Center** studies:

Check to see if all software applications used in this study are already on the [list of approved software](#). Please review the version type and/or described use-case of each application to confirm approved use. If the software you are using is not already on the [list of approved software](#) (or will not be used in accordance with the approval details on the list), you are required to complete this [IT Security form](#) so Tufts Medical Center can review the security of the software.

Check this box if the [IT Security form](#) has been completed and submitted.

Check this box if you have confirmed that the software applications used in this study are already on the [list of approved software](#) (and will be used in accordance with the details on the list)

Please e-mail [contact] with any questions about this institutional requirement.

5. *Will data (or specimens) be sent outside of Tufts Medical Center or Tufts University and/or sent between Tufts Medical Center and Tufts University?*
 Yes No
6. *Explain how data and/or specimens will be transported (e.g. fax, mail, delivery, email, etc.):*
Data will be kept and transported by hand only by members of the investigator team. Electronic data will be accessed via secure internet and Tufts VPN usage with Tufts CTSI REDCap and Box cloud storage.
7. *If data and/or specimens will be coded, describe the coding mechanism in detail. Describe how the unique IDs (used to code the data) will be generated / assigned (sequential, random, other). If not sequential, explain how you will avoid duplicates:*

Each patient will be assigned a 3-digit numerical code. These codes will be from a randomly generated list of 66 codes (given the maximum target of 66 patients for the study) using an online randomizing tool, which will also separate these 66 values into two lists of 33 values (one for each treatment arm). A separate list of 66 values will be generated to randomize patients into one of the two treatment arms using the same online software. Patients will then be sequentially assigned their random 3-digit identifiers in the order of recruitment.

Note: The IDs used to code the data should not include initials, dates, or any identifiers.

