1. *Describe the sites / locations where your research team will conduct the research, including recruitment activities:*
 - a. *Tufts MC / Tufts University locations (specify which facility/clinic if applicable):*
Tufts Medical Center, Labor and Delivery Unit

K.2 Registration

1. *Describe the steps the research team will take to ensure that a subject is appropriately enrolled or registered in the study prior to receiving any study intervention (e.g. describe and submit any protocol eligibility checklist that will be used, specify who on the research team will confirm eligibility and that consent was documented, etc.):*
The Co-I will ensure subject eligibility, perform the informed consent process, and subsequently perform the study protocol. Eligibility criteria will be consistent with those outlined above in Section D. Thus, there will be no risk of miscommunication between the informed consent process and the study interventions.

K.3 Resources Available

1. *Describe the roles/tasks of each research team member here (or alternatively, you may submit any current Delegation of Authority Log you may have which already has this information completed):*
The research team is composed of the following members:
 - Principal investigator: [name] Assistant professor of Anesthesiology. Primary investigator responsible for the preparation, design, conduct, and administration of the study.
 - Co-investigator: [name], MS4 and Tufts CTS Research Fellow. Responsible for writing the study's protocol under the PI guidance, obtaining the informed consent, managing data collection, and coding and coordinating various sectors in the study.
 - Tufts Medical Center facilities will provide medical resources that might be needed by study subjects.
2. *Describe the qualifications (e.g., training, experience) of the PI and research team to perform their roles. Provide enough information for the IRB to determine the PI and research team are qualified to conduct the proposed research. Alternatively, you can submit the current CVs for the research team instead:*
 - Please see attached CVs
3. *Describe the coverage plan to address any issues (including subject safety issues) that occur while the PI is away and/or unavailable. The research team member designated to serve as the acting PI in the PI's absence should have similar training and expertise as the PI:*

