In the absence of the PI, the Co-I will perform duties as able but may temporarily halt research activity until the PI's return if necessary. This is due to the fact that the Co-I has some similar training to that of the PI but not to the same extent (less overall research and clinical experience). If patient safety issues arise while the PI is absent, the Co-I would temporarily halt research activity until the PI's return.
4. *Describe the process to ensure the research team members have adequate oversight and are adequately trained regarding the protocol, study procedures, and their roles and responsibilities:*
There will only be two research team members, the PI and the Co-I, both of whom will be heavily involved and educated on the study protocol, procedures, and their respective roles and responsibilities.
5. *Medical or psychological resources that subjects might need, such as for emergencies or medical issues, are available for the study:* Yes N/A

K.4 IRB Review

1. *Check to confirm that an appropriate IRB, registered with the OHRP, will review and approve this study.*
2. *Check to confirm that any amendments to the protocol or informed consent documents will be reviewed and approved by the IRB prior to use, unless required to eliminate an apparent immediate hazard to subjects.*

K.5 Multi-Site Research

Is this a multi-site study where Tufts IRB is requested to be the Single IRB of record for non-Tufts sites or collaborators, AND/OR where Tufts is the sponsor, primary grant recipient, or coordinating site?:

Yes No

K.6 Community-Based Participatory Research

Can or will this study involve community-based participatory research?

Yes No

K.7 Sharing Results with Subjects

Will results (overall study results or individual subject results, such as results of investigational diagnostic tests, genetic tests, or incidental findings) be shared with subjects or others (e.g., the subject's primary care physician or the subject's treating physician)?

Yes No

L. Nursing Involvement

Will your study require the involvement of Nursing

Yes No

If Yes, respond to all of the following:

1. Describe the research procedures Nursing will do for this study above and beyond their usual nursing practice:
Nursing may assist in acquiring vitals for this study if it coincides with their usual nursing practices.
Nursing is otherwise only asked to help coordinate clinical care with the research procedures that will be carried out by investigators.

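### The plan describes no allocation concealment: the two-person team that enrols also has access to the arm list made in advance, so the recruiter can know the next arm.

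*Combined protocol and SAP*

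**What the plan says.** **Who enrols and delivers.** K.2 states: "The Co-I will ensure subject eligibility, perform the informed consent process, and subsequently perform the study protocol". K.3 adds that the Co-I is responsible for "obtaining the informed consent, managing data collection, and coding and coordinating various sectors in the study". D.2 is wider: "Either the PI or Co-investigator will determine final eligibility". G.1 likewise lets either person take consent. K.3 closes the circle: "There will only be two research team members, the PI and the Co-I".

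**How the arm is assigned.** G.3 (item 7) has the three-digit codes generated at random and split into two sets of 33, one per arm. It continues: "A separate list of 66 values will be generated to randomize patients into one of the two treatment arms using the same online software". Then: "Patients will then be sequentially assigned their random 3-digit identifiers in the order of recruitment". I.5 gives a 1:1 ratio and says that duration follows a biased-coin up-down rule. G.3 (items 1 and 3) restricts study files to the research team.

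**What is hidden, and from whom.** I.5 says that the person giving the intervention and the anxiety assessment cannot be blinded. The only blinding before the intervention is the participant's: "However, the participants will remain blind to their randomized intervention group until the intervention begins". F.2 has every participant list four songs first, to be "later used if their pre-determined music selection falls into the" personal-preference arm.

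**Exclusion after consent.** Under D.2, D.3 and F.2, a baseline anxiety score of 0, collected by the investigator after consent, removes the participant. D.3 then has that person's data destroyed.

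**The concern.** Blinding and concealment are different things. An open-label trial can still keep the next assignment unknown until a participant is irrevocably in. I.5 explains why blinding is not feasible but does not address concealment. Followed as written, the plan leaves the arm list within reach of the people who approach patients, judge eligibility, take consent and record the score that can still remove someone.

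If the next arm is known, the choice of whom to approach, when to approach, and how to apply a judgement-based criterion can depend on it. Exclusion 6 in D.2 (fetal conditions or other pregnancy complications, with an open-ended list of examples) is such a criterion. The comparison of ED95 between the Mozart and preferred-music arms relies on randomisation for comparable groups, and selection of this kind removes that protection. Because the data of withdrawn participants are destroyed, an uneven pattern of score-0 removals could not be found afterwards.

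**Working it through.** **1. The plan's own figure.** I.2 gives 33 per arm for 30 completers at about 10% attrition. 30 × 1.10 = 33, and 33 × 0.90 = 29.7. Dividing instead, 30 / 0.90 = 33.3, gives 34. The figure reproduces within rounding, and this point does not depend on it.

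**2. Is any concealment step described?** G.3 covers generation and order of use, I.5 covers ratio and blinding, K.2 covers registration, and F.2 covers the sequence of procedures. None mentions sealed envelopes, a locked allocation module, a list holder outside the team, or release of the arm after baseline. Whether the enroller is the Co-I alone (K.2) or either investigator (D.2, G.1), that person belongs to the pair with file access.

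**3. Predictability of the next arm.** The inputs are 66 assignments, 33 per arm (G.3, I.2).
- List accessible: up to 66 of 66 known, or 100%.
- List concealed, unblocked 33/33, recruiter always guessing the arm with more places left: expected correct guesses = n + 4^n / (2 × C(2n, n)) − 1/2. With n = 33 this is 33 + 2^65 / C(66, 33) − 0.5 = 37.6, and 37.6 / 66 = 57.0%. A simulation of 20,000 lists gave 57.0%.

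The gain from concealment is therefore from as much as 100% down to about 57%.

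**4. Predictability of the next duration.** The protocol gives no coin probability, so the standard ED95 rule is assumed: b = (1 − 0.95) / 0.95 = 0.0526. After a failure the step up is certain. After a success the duration stays the same with probability 1 − 0.0526 = 94.7%. At the target the overall figure is 0.05 × 1 + 0.95 × 0.947 = 95%. Whoever records the responses can thus largely foresee each arm's next duration even when the arm list is hidden. Hiding the arm leaves uncertain only which sequence applies, and only when the two durations differ.

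**5. Illustration of imbalance.** Assume a normally distributed baseline score. Let a share s of candidates on the unwanted side of the median be turned away, in opposite directions for the two arms. The difference in baseline means, in SDs of the unselected score, is 2 × √(2/π) × s / (2 − s). For s = 10%, 20% and 30% this gives 0.08, 0.18 and 0.28. The documents contain no value of s, so this shows scale only.

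**The case against.** Much of the case on the other side stands.

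- **A reader might infer that the Co-I holds the list.** No sentence says so. G.3 describes list generation without naming a holder, and K.3 gives the PI responsibility for conduct and administration. What the documents support is access by a two-person team and no described safeguard.
- **A reader might take the word pre-determined in F.2 to mean that the investigator knows the arm at screening.** It shows that selection and duration are fixed before the music starts. It does not say when the investigator learns them.
- **Room for steering is limited.** Age, ASA status and daily anxiolytic use are checked from the chart. The 0–10 score is the participant's own rating, given while blind to arm; the investigator records it. Under D.4.1, obstetric staff mention the study and a provider alerts the team when a patient is interested, although the same section also says that the team recruits directly and daily.
- **A reader might convert the concern into minutes of ED95.** B.1 reports that as few as 4 minutes gave a 1-point fall, which invites a slope of 0.25 point per minute. That is one preliminary observation, not a slope. ED95 is a quantile of a success/failure response, and the documents give neither its dose-response curve nor a size for any steering.

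None of this supplies a concealment step. It limits the likely harm but leaves the gap open.

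**Conclusion.** The concern holds in this form: the plan describes no allocation concealment, and the recruiter can know the next arm. The size that can be stated is predictability, up to 66 of 66 as planned against about 37.6 of 66 (57%) with a concealed list. The 57% assumes an unblocked list with exactly 33 per arm and a recruiter who tracks the running counts.

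The consequence is possible bias, mainly in the secondary between-arm ED95 comparison. Each arm's own ED95 is exposed less directly, through durations that the team can foresee in any case. The documents do not show that steering is likely, and they do not support a claim that the primary result is biased by any stated amount. This is a procedure that the plan should change, at small cost; it does not invalidate the design.

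**What to change.** In I.5 and K.2, state the following.

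1. The arm list is generated, and loaded into the randomisation module of REDCap (already used under G.3), by the team member who does not enrol, for example the PI, or by REDCap support. The person who screens, consents and takes baseline has no access to it.
2. D.2 and G.1, which let either person enrol, are reconciled with this.
3. The arm is released only after eligibility, consent, the 0–10 score, STAI, vital signs and song list are entered and locked. Because G.3 splits the three-digit codes by arm, a code seen before that point must not reveal the arm.
4. The duration is then taken from that arm's running up-down sequence.
5. A coded count of score-0 removals is kept, with D.3 worded so that the count survives the destruction of individual data.

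The costs are a short log-in step at the bedside, the REDCap set-up and a few sentences of text. Whoever loads the list cannot enrol, which in a two-person team leaves one enroller unless REDCap support does the loading. Concealment of duration remains partial: the recruiter still knows each arm's likely next duration and is uncertain only about which arm applies when the two differ.
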